11.2 Recording of an Adverse Event

All adverse events will be entered into OnCore®, UCSF"s Clinical Trial Management System, whether or not the event is believed to be associated with use of the investigational drug. Data about these events and their severity will be recorded using the NCI Common Terminology Criteria for Adverse Events (CTCAE) (V4.0), when applicable, on the appropriate case report forms (CRFs). The Investigator will assign attribution of the possible association of the event with use of the investigational drug, and this information will be entered into OnCore using the classification system listed below:

Relationship	Attribution	Description
Unrelated to	Unrelated	The AE is clearly NOT related to the intervention
investigational agent/intervention	Unlikely	The AE is doubtfully related to the intervention
Related to	Possible	The AE may be related to the intervention
investigational	Probable	The AE is likely related to the intervention
agent/intervention1	Definite	The AE is clearly related to the intervention

Signs or symptoms reported as adverse events will be graded and recorded by the Investigator according to the CTCAE. When specific adverse events are not listed in the CTCAE they are to be graded by the Investigator as none, mild, moderate or severe according to the following grades and definitions:

- Grade 0: No AE (or within normal limits).
- Grade 1: Mild; asymptomatic or mild symptoms; clinical or diagnostic observations only; intervention not indicated.
- Grade 2: Moderate; minimal, local, or noninvasive intervention (e.g., packing, cautery) indicated; limiting age-appropriate instrumental activities of daily living (ADL).
- Grade 3: Severe or medically significant but not immediately life-threatening; hospitalization or prolongation of hospitalization indicated; disabling; limiting self-care ADL.
- Grade 4: Life-threatening consequences; urgent intervention indicated.

Grade 5: Death related to AE.

11.3 Follow-up of Adverse Events

All adverse events must be followed with appropriate medical management until resolved. For selected adverse events for which administration of the investigational drug was stopped, a re-challenge of the subject with the investigational drug may be conducted if considered both safe and ethical by the Investigator.

11.4 Serious Adverse Events Monitoring

All serious adverse events, whether or not unexpected, and whether or not considered to be associated with the use of the study drug, will be entered into OnCore®, as noted above.

The Principal Investigator will assess each Serious Adverse Event (SAE) and determine reportability requirements to the Data and Safety Monitoring Committee (DSMC), UCSF's Committee on Human Research (CHR), and, when the study is conducted under an Investigational Drug Application (IND), to the Food and Drug Administration.

All serious adverse events entered into OnCore® will be reviewed by the Site Committee on a weekly basis. The Site Committee will review and discuss at each weekly meeting the selected toxicity, the toxicity grade, and the attribution of relationship of the SAE to the administration of the study drug(s).

In addition, all serious adverse events entered into OnCore® will be reviewed and monitored by the Data and Safety Monitoring Committee on a monthly basis and prior to dose escalation. At the time of dose escalation, a written report will be submitted to the DSMC Chair outlining the cohorts, dose, AEs and SAE reports, and any Dose Limiting Toxicities observed, in accordance with the protocol. The report will be reviewed and approved by the DSMC Chair (or designee) prior to dose escalation.

11.5 Serious Adverse Events Expedited Reporting

Reporting to the Data and Safety Monitoring Committee (DSMC)

If a death occurs during the treatment phase of the study or within 30 days after the last administration of the study drug(s) and it is determined to be related either to the study drug(s) or to a study procedure, the Investigator or his/her designee must notify the DSMC Chair within 24 hours of knowledge of the event. The contact may be by phone or e-mail.

Reporting to the Committee on Human Research (CHR)

The Investigator must report SAEs meeting the CHR definition of "Unanticipated Problem" (UP) within 10 working days of his/her awareness of the event.

Specific instructions on SAE reporting may be found at the UCSF CHR website at: http://www.research.ucsf.edu/chr/Guide/Adverse_Events_Guidelines.asp

Expedited Reporting to the IND

If the study is being conducted under an Investigational Drug Application, the Sponsor-Investigator is responsible for determining whether or not the SAE meets the criteria for expedited reporting in accordance with Federal Regulations (21 CFR §312.32).

The Investigator must report in an IND safety report any suspected adverse reaction that is both serious and unexpected. The Sponsor-Investigator needs to ensure that the event meets all three definitions:

- Suspected adverse reaction
- Serious
- Unexpected

If the adverse event does not meet all three of the definitions, it should not be submitted as an expedited IND safety report.

The timeframe for submitting an IND safety report to FDA is no later than 15 calendar days after the Investigator determines that the suspected adverse reaction qualifies for reporting (21 CFR 312.32(c)(1)).

Any unexpected fatal or life-threatening suspected adverse reaction must be reported to FDA no later than 7 calendar days after the Investigator's initial receipt of the information (21 CFR 312.32(c)(2)).

Any relevant additional information that pertains to a previously submitted IND safety report must be submitted to FDA as a Follow Up IND Safety Report without delay, as soon as the information is available (21 CFR 312.32(d)(2)).

For additional information and guidance on IND Safety Reports, please refer to the FDA Guidance for Industry: Safety Reporting Requirements for INDs.

12.0 Study Management

Pre-study Documentation

This study will be conducted in accordance with the ethical principles that have their origin in the Declaration of Helsinki as stated in 21 CFR 312.120(c)(4); consistent with GCP and all applicable regulatory requirements.

Prior to implementing this protocol at UCSF HDFCCC, the protocol, informed consent form, HIPAA authorization and any other information pertaining to participants must be approved by the UCSF Committee on Human Research (CHR). Prior to implementing this protocol at the participating sites, approval for the UCSF CHR approved protocol must be obtained from the participating site"s IRB.

The following documents must be provided to UCSF HDFCCC before the participating site can be initiated and begin enrolling participants:

- Participating Site IRB approval(s) for the protocol, appendices, informed consent form and HIPAA authorization
- Participating Site IRB approved consent form
- Participating Site IRB membership list
- Participating Site IRB"s Federal Wide Assurance number and OHRP Registration number
- Curriculum vitae and medical license for each investigator and consenting professional
- Documentation of Human Subject Research Certification training for investigators and key staff members at the Participating Site
- Participating site laboratory certifications and normals

Upon receipt of the required documents, UCSF HDFCCC will formally contact the site and grant permission to proceed with enrollment (a detailed listing of the documents required from participating sites is provided in Appendix 4).

The clinical investigation will not begin until either FDA has determined that the study under the Investigational Drug Application (IND) is allowed to proceed or the Investigator has received a letter from FDA stating that the study is exempt from IND requirements.

The Investigator must comply with the applicable regulations in Title 21 of the Code of Federal Regulations (21 CFR) Parts §50, §54, and §312, GCP/ICH guidelines, and all applicable regulatory requirements. The IRB must comply with the regulations in 21 CFR 56 and applicable regulatory requirements.

Institutional Review Board Approval

The protocol, the proposed informed consent form, and all forms of participant information related to the study (e.g. advertisements used to recruit participants) will be reviewed and approved by the Committee on Human Research (UCSF"s IRB). Prior to obtaining CHR approval, the protocol must be approved by the Helen Diller Family Comprehensive Cancer Center Protocol Review Committee (PRC). The initial protocol and all protocol amendments must be approved by the IRB prior to implementation.

Informed Consent

All participants must be provided a consent form describing the study with sufficient information for participants to make an informed decision regarding their participation. Participants must sign the IRB-approved informed consent form prior to participation in any study specific procedure. The participant must receive a copy of the signed and dated consent document. The original signed copy of the consent document must be retained in the medical record or research file.

Changes in the Protocol

Once the protocol has been approved by the UCSF Committee on Human Research (CHR), any changes to the protocol must be documented in the form of an amendment. The amendment must be signed by the Investigator and approved by PRC and the CHR prior to implementation. If it becomes necessary to alter the protocol to eliminate an immediate hazard to patients, an amendment may be implemented prior to CHR approval. In this circumstance, however, the Investigator must then notify the CHR in writing within five (5) working days after implementation.

Handling and Documentation of Clinical Supplies

The Investigator shall maintain complete records showing the receipt, dispensation, return, or other disposition of all investigational drugs. The date, quantity and batch or code number of the

drug, and the identification of patients to whom study drug has been dispensed by patient number and initials will be included.

The Investigator shall not make the investigational drug available to any individuals other than to qualified study patients. Furthermore, the Investigator will not allow the investigational drug to be used in any manner other than that specified in this protocol.

Case Report Forms (CRFs)

The Principal Investigator and/or his/her designee will prepare and maintain adequate and accurate participant case histories with observations and data pertinent to the study. Study specific Case Report Forms (CRFs) will document treatment outcomes for data analysis. All study data will be entered into OnCore®, UCSF"s Clinical Trial Management System (CTMS) via standardized CRFs in accordance with the CTMS study calendar, using single data entry with a secure access account. The Clinical Research Coordinator (CRC) will complete the CRFs as soon as possible upon completion of the study visit; the Investigator will review and approve the completed CRFs.

The information collected on CRFs shall be identical to that appearing in original source documents. Source documents will be found in the patient"s medical records maintained by UCSF personnel. All source documentation should be kept in separate research folders for each patient.

In accordance with federal regulations, the Investigator is responsible for the accuracy and authenticity of all clinical and laboratory data entered onto CRFs. Each CRF must be reviewed for accuracy by the Investigator, corrected as necessary, and then approved. Alternatively, the Investigator may sign individual, printed CRFs. These signatures attest that the information contained on the CRFs is true and accurate.

All source documentation and CTMS data will be available for review/monitoring by the Data and Safety Monitoring Committee (DSMC) and regulatory agencies.

The Principal Investigator will be responsible for ensuring the accurate capture of study data. At study completion, when the database has been declared to be complete and accurate, the database will be locked. Any changes to the database after that time can only be made by joint written agreement among the Principal Investigator, the Trial Statistician, and the Protocol Project Manager.

Oversight and Monitoring Plan

The Helen Diller Family Comprehensive Cancer Center Data and Safety Monitoring Committee (DSMC) will be the monitoring entity for this study. The DSMC will monitor the study in accordance with the NCI-approved Data and Safety Monitoring Plan (DSMP). The Data and

Safety Monitoring Plan for Multicenter Institutional Study (Phase 2 or 3) is described in Appendix 4. The DSMC will audit study-related activities to ensure that the study is conducted in accordance with the protocol, local standard operating procedures, FDA regulations, and Good Clinical Practice (GCP). In addition, the DSMC will regularly review serious adverse events and protocol deviations associated with the research to ensure the protection of human subjects. Results of the DSMC audit will be communicated to the IRB and the appropriate regulatory authorities at the time of continuing review, or in an expedited fashion, as applicable.

Retention of Records

The Investigator will retain a copy of all study documents in accordance with FDA regulations:

- for a minimum of two years following the date a marketing application (New Drug Application or NDA) is approved for the drug for the proposed clinical indication; or
- if no marketing application is filed, or if the marketing application has been filed but is not approved by the FDA, then for a minimum of two years following the release date of the final report; or

The Investigator agrees to maintain a complete and current record of all documentation associated with the study. All of the documents shall be kept together. Each should be available for ready review. These study documents will include the:

- protocol
- protocol amendments, when applicable
- signed FDA Form 1572
- Investigator"s current curriculum vitae
- documentation of CHR approvals for the protocol, amendments, informed consents and advertisements used to recruit patients
- Investigator's Brochure(s)
- site visit log
- correspondence (all "to" and "from" correspondence)
- drug accountability records, drug shipment forms, and drug disposal records
- case report forms and informed consent documents for individual patients
- final report for the study if available.

13.0 Protection of Human Subjects

Protection from Unnecessary Harm

Each clinical site is responsible for protecting all subjects involved in human experimentation. This is accomplished through the CHR mechanism and the process of informed consent. The CHR reviews all proposed studies involving human experimentation and ensures that the subject"s rights and welfare are protected and that the potential benefits and/or the importance of the knowledge to be gained outweigh the risks to the individual. The CHR also reviews the

informed consent document associated with each study in order to ensure that the consent document accurately and clearly communicates the nature of the research to be done and its associated risks and benefits.

Protection of Privacy

Patients will be informed of the extent to which their confidential health information generated from this study may be used for research purposes. Following this discussion, they will be asked to sign the HIPAA form and informed consent documents. The original signed document will become part of the patient"s medical records, and each patient will receive a copy of the signed document. The use and disclosure of protected health information will be limited to the individuals described in the informed consent document.

Appendix 1. List of Prohibited Medications and Supplements While Patients Are Taking Itraconazole

Abiraterone acetate Amiodarone Astemizole Atorvastatin Bicalutamide Chemotherapy Cisapride Cyproterone acetate Diethylstilbesterol Degarelix Dofetilide Dutasteride Enzalutamide (MDV3100) Eplerenone Ergot alkaloids Estrogens Felodipine Finasteride Fluconazole Flutamide **GM-CSF** Goserelin Ketoconazole Levomethadyl Leuprolide acetate Lovastatin Megestrol Methadone Midazolam Milk thistle Nilutamide Nisoldipine Other investigational agents PC-SPES Pimozide Pomegranate extract Pomegranate juice Progesterones Ouinidine Radiation therapy Saw palmetto Simvastatin Sipuleucel-T Spironolactone Steroids at an equivalent dose of prednisone 5 mg per day or higher Phase II - Itraconazole

Version 4.0: October 8, 2014 Terfenadine Triazolam

Appendix 2. Potential Drug-Drug Interactions

CYP3A4 Iuductrs (drug, s that decrease the bioavailability of itraconazole)

- Aminoglutethimide
 Barbiturates
 Carbamazepine
 Efavirenz
 Glucocorticoids
 Modafinil
- 7. Nafcillin
 8. Nevirapine
 9. Oxcarbazepine
 10. Phenobarbital
 11. Phenytoin
 12. Pioglitazone
- 13.Rifabutin 14.Rifampin 15.StJohn's wort 16.Troglitazoue

CYP3A4 Inhibitors (drues that increase the bioavailability of itraconazole)

- I. Amiodarone * 9. Grapefruit juice 2. Aprepitant 10. Indinavir 3.Cimetidine Isoniazid 4. Clarithromycin 12. Ketoconazole 5. Diltiazem 13. Mibefradil 6. Erythromycin 14. Nefazodone 7.Fluconazole IS Nelfinavir 8. Fluvoxantine 16. Nortloxacin
- 17. Ritonavir18. Saquinavir19. Telithromycin20. Troleandomycin21. Veraparnil22. Voriconazole

CYP3A4 Substrates (drug,s whose bioavailability may increase with itraconazole use)

19. Erythromycin I. Alprazolam 2. Amiodarone * 20. Felodipine 3. Amlodipine 21. Fentanyl 4. Aripiprazole 22. Glucocorticoids 5. Astemizole • 23. Haloperidol 6. Atorvastatin • 24. Inlatinib 25 Indinavir 7. Buspirone 8. CWorpbenirantine 26. Levacetylmetl:adol • 27. Lovastatin • 9. Cilostazol I0. Cisapride • 28. Methadone 29. Midazolam * II. Clarithromycin 30. Mirtazapine 12. Cyclosporine 13. Diazepam 31. Nateglinide 14. Digoxin 32. Nifedipine 15. Diltiazem 33. Nisoldipine 16. Disopyrarnide 34. Nitrendipine 17. Dofetilide • 35. Oral hypoglycernics 36. Pimozide • 18. Ergot alkaloids *

37.Quinidine • 38.Quinine 39. Ritonavir 40. Saquinavir 41. Sildenafil 42 Simvastatin • 43. Sirolinms 44. Tacrolimus 45. Tamoxifen 46. Telithromycin 47. Terfenadine • 48. Trazodone 49. Triazolam * 50.Veraparnil 51. Vinca alkaloids 52. Warfarin

• These drugs are absolutely *contraindicated* in patients taking concurrent itraconazole. The remainder maybe used with caution.

Appendix 3. Skin Biopsy Procedure and Specimen Handling Shipping Instructions for Serum and Tissue Specimens

There are three categories of specimens for this trial which will be shipped to a central processing site: skin biopsies, archived primary prostate cancer tissue (radical prostatectomy or biopsy specimens), and peripheral blood collected for serum drug levels. Serum hormone levels will be analyzed locally at each participating institution.

I. Skin Biopsy Procedure, Processing, and Shipping Instructions

For patients enrolled at UCSF, the skin biopsies will occur at the Helen Diller Family Comprehensive Cancer Center. Skin biopsies will be obtained twice for each patient who signs additional consent to participate in this correlative study: (1) pre-study (within 6 weeks of Day 1 of protocol therapy) and (2) at 28 days (+/- 7 days) of protocol therapy.

Specimen Requirements: A 3 mm skin punch biopsy (to the level of the subcutaneous tissue) should be obtained from an area of non-scalp skin with hairs and/or hair follicles. The upper back and arms are the preferred biopsy sites. Subsequent biopsies should be taken from the same general area of the body. Skin biopsies should be performed according to standard local protocols. One example is the following: the biopsy site should be cleaned and prepped using sterile technique, and anesthetized with 1-2% lidocaine with epinephrine. The biopsy should be performed using a sterile 3 mm punch biopsy tool. The biopsy site may be closed with steristrips, or with one or two sutures, and a sterile dressing may be applied. The skin biopsy sample should be placed immediately into a 5 ml Tissue Protect Tube containing RNAlater solution (Ambion, catalog # AM7023). Care must be taken to ensure that the skin sample is fully submerged in RNAlater. RNAse Zap spray should *not* be used on gloves or the work surface during skin biopsy collection.

Processing Instructions: The sample should be kept at 4°C overnight (for ≥ 12 hours) so that RNAlater can seep into the tissue. The sample should then be frozen at -20°C or colder until the time of transport, and should be shipped to the analyzing lab on dry ice (see below). The sample is stable for 5 days at room temperature, for one month at 4°C, and for one year at -20°C. Once received by the analyzing lab, the sample should be stored at -20°C or colder until the time of RNA extraction.

Comments: The date and time of collection should be recorded on the Biomarkers Worksheet. Tissue Protect Tubes should be labeled with patients" initials, identification number, biopsy site, date, time, study number, and protocol day.

Shipping Instructions: Skin *GLI1*mRNA analysis will be performed at Johns Hopkins in the research laboratory of [name], PhD, under the direction of [name],

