9.2 Hedgehog Pathway Assessment BymRNA Expression Analysis

Because Hedgehog signaling is present in skin and hair follicles, *GL11* mRNA expression (a marker of Hedgehog pathway activation) will be analyzed using 3-millimeter skin punchbiopsies from hair-containing non-scalp skin (e.g. upper back or arms) obtained at baseline and after 4 weeks on study, using previously described and validated methodology [25]. The skin sample should be placed immediately into a 5 mL Tissue Protect Tube containing RNAlater solution, and care must be taken to ensure that the skin sample is fully submerged in RNAlater. Samples should then be frozen at -20 degrees Celsius or colder until the time of RNA extraction. Additionally, mRNA expression analysis of archived, formalin-fixed paraffin embedded primary prostate cancer tissue will be performed when tissue is available. Please see Appendix 3 for details regarding the skin biopsy procedure as well as specimen handling/shipping instructions.

*GLI1*mRNA expression levels in tissue samples will be analyzed using the RT² Profiler Custom PCR Array protocol (SABiosciences, Qiagen). RNA will be extracted from tissue samples using RNeasy Fibrous Tissue kit (Qiagen). The RT² PCR Array First Strand kit (SuperArray Bioscience), will be used to synthesize cDNA. Quantitative PCR will be performed using RT² Real-Time SYBR Green PCR Master Mix (SABiosciences, Qiagen), in an ICycler PCR System (Bio-Rad Laboratories), according to the manufacturer's protocol. The housekeeper gene *GAPDH* will be used, as the expression level of this gene has been previously shown to not change with itraconazole therapy using a housekeeper array (Cat#: PHAS-000, SABiosciences, Qiagen). Cycling threshold (C_t) values for *GLI1*and *GAPDH* from each experiment will be analyzed using the SABiosciences software and fold change of *GLI1*expression, normalized to *GAPDH*, will be derived for each sample.

Patients will be dichotomized for the purposes of statistical analysis. The full statistical analytic plan for *GLI1* expression datais described in Section 10.

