10.8.3 Analytic Plan for the Correlative Objectives

Endocrine Parameters

Serum hormone levels, including testosterone, androstenedione, DHEA-S, cortisol, aldosterone, 11-deoxycortisol, ACTH, and deoxycorticosterone, will be measured at baseline, at week 4, week 12, and at the time of PSA or clinical progression. To summarize the outcome, descriptive statistics including the mean percent change from baseline in serum hormone levels at 4 and 12 weeks will be presented with a standard deviation and Pearson"s correlation will be used to estimate the relationship between the baseline hormone level and percent change in hormone level after 4 and 12 weeks of treatment. Analysis of variance (ANOVA) methods for mixed models allowing for variable number of follow-up measurements with linear contrasts will be used to evaluate the change in serum hormone levels after 4 and 12 weeks of protocol therapy. It is hypothesized that approximately 15% of patients treated with protocol therapy will achieve a PSA decline \geq 50%. Depending upon the observed frequency, the ANOVA model will include a factor to test for the effect of PSA decline on change in serum hormone levels. Otherwise, analyses will compare the baseline and percent change in serum hormone levels at 4 and 12 weeks between patients achieving a PSA decline $\geq 50\%$ or not using a two group t statistic. For these exploratory analyses, graphic presentations will also be used to explore the overall pattern of change in serum hormone levels between those with and without a PSA decline.

Hedgehog Pathway

The quantitative expression of *GLI1*, a downstream product of the Hedgehog signal transduction pathway, will be measured by quantitative RT-PCR from serial skin biopsies obtained at baseline and after 4 weeks of therapy. The fold change in expression level after 4 weeks of protocol therapy will be calculated for each patient. Descriptive statistics will be used to summarize the proportion of patients with down-regulation of *GLI1* expression after 4 weeks of treatment with itraconazole. Down-regulation will be defined as any magnitude of decrease in *GLI1* mRNA expression after 4 weeks of protocol therapy compared to baseline expression level. The patient

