cohort will be dichotomized by whether there is up- or down-regulation of *GL11* expression. Fisher's exact test will be used to test for an association between down-regulation of *GL11* expression and PSA decline 50% on protocol therapy. The probability distributions for each *GL11* expressionsubset (as defined above) of the time to PSA progression will be estimated using the Kaplan-Meier product limit method. The results will be summarized by the estimated median with 95% confidence intervals. An exploratory analysis using the log-rank test will be used to test for differences in the distributions between patients with down-regulation of *GL11* expression vs. those without *GL11* down-regulation on therapy.

The quantitative expression of *GLI1* will also be measured by quantitative RT-PCR from archived primary prostate cancer tissue. The patient cohort will be dichotomized by expression level of *GLI1* (above vs. below the median). Fisher's exact test will be used to test for an association between *GLI1* expression in primary prostate cancer tissue and PSA decline $\geq 50\%$ on itraconazole therapy. The probability distributions for each *GLI1* expression subset of the time to PSA progression will be estimated using the Kaplan-Meier product limit method. The results will be summarized by the estimated median with 95% confidence intervals. An exploratory analysis using the log-rank test will be performed to test for differences in the distributions between patients with *GLI1* expression above vs. below the median from primary prostate cancer tissue specimens.

Immunohistochemical analysis of primary prostate cancer tissue for protein expression of *PCTH1*, *GL11*, *SMO*, as well as Sonic hedgehog ligand will be carried out for patients with evaluable tissue. It is estimated that approximately 50% of patients will have tissue available for analysis. Immunohistochemical expression will be graded as 0, 1+, 2+, and 3+ staining intensity by independent, blinded pathologic assessment. For each protein, the patient cohort will be dichotomized based on intensity of IHC staining (0 and 1+ vs. 2+-3+). Fisher''s exact test will be used to test for an association between IHC expression and PSA decline > 50% on protocol therapy. The probability distibutions for each expression subset of the time to PSA progression will be estimated using the Kaplan-Meier product limit method. The results will be summarized by the estimated median with 95% confidence intervals.

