Samples arriving from outside institutions should be shipped on dry ice (a minimum of 5 kg) using overnight shipping to [name] in the Specimen Accessioning Core (SAC) laboratory at Johns Hopkins, at the address below. Overnight shipments should occur on Monday through Thursday, except when the following day is a holiday. A fax or call should be placed to the SAC laboratory prior to shipment, providing the shipment tracking information.

[name] Specimen Accessioning Core (SAC) Johns Hopkins Hospital Attn: Itraconazole Study Samples [name] [contact] or [contact] [contact] [contact] Email: [contact]

IV. Processing and Shipping of Serum Hormone Levels

Peripheral blood for measurement of serum testosterone, cortisol, aldosterone, deoxycorticosterone, 11-deoxycortisol, adrenocorticotropic hormone (ACTH). dihydroepiandrostenedione-sulfate (DHEA-S), and androstenedionewill be collected at each site according to the instructions outlined below, and shipped to UCSF for analysis. Specimens should be shipped within 1 month of date of collection.

Peripheral blood collection for banking of peripheral blood mononuclear cells, plasma, and serum is optional. Specimens will be banked at UCSF-HDFCCC Tissue Bank.

A. Patient Confidentiality

Prior to the date of collection of each sample to be shipped to UCSF, the local CRC should notify the lead center CRC that specimen is to be collected at the patient's next visit. The lead center CRC will then assign unique specimen log numbers to be written on the specimen vials; this will ensure patient confidentiality.

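### Skin-biopsy tubes for the GLI1 assay show the protocol day, and the available text states no recoding, masking or same-run pairing for an endpoint where any decrease counts

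*Combined protocol and SAP*

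**What the plan says.** Appendix 3, section I, asks for two 3 mm punch biopsies from each man who gives the extra consent: "1) pre-study (within 6 weeks of Day 1 of protocol therapy) and (2) at 28 days (+/- 7 days) of protocol therapy". Each tube is labelled with the patient's "initials, identification number, biopsy site, date, time, study number, and protocol day". For skin GLI1, the "mRNA analysis will be performed at Johns Hopkins in the research laboratory of" a named investigator. On storage the appendix says: "Once received by the analyzing lab, the sample should be stored at -20°C or colder until the time of RNA extraction".

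Section 9.2 describes the assay. Ct values for GLI1 and GAPDH "will be analyzed using the SABiosciences software and fold change of" GLI1, normalised to GAPDH, is derived for each sample. It states no masking, assay order, same-run pairing or rerun rule. Section 10.8.3 sets the threshold: "Down-regulation will be defined as any magnitude of decrease in" GLI1 expression at week 4 against baseline. The resulting two groups are compared on PSA response (Fisher's exact test) and on time to PSA progression (exploratory log-rank test).

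Two other places use related safeguards. Archived-tissue staining is graded "by independent, blinded pathologic assessment" (10.8.3), which section 9.3 specifies as blinding to clinical outcomes. For samples shipped to UCSF, Appendix 3, IV.A, has the lead-centre coordinator "assign unique specimen log numbers to be written on the specimen vials; this will ensure patient confidentiality".

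**The concern.** A within-patient comparison is best read by people who do not know which sample came first. Here the label gives the visit, and nothing in the assay or analysis sections takes that information away before measurement. The readout is an instrument value, but a laboratory still decides whether to repeat a run, whether to drop a poor sample and which samples share a plate. With no minimum fold change, a small displacement in either direction can change a man's category.

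Skin GLI1 is the only on-treatment measure of the Hedgehog pathway; the archived tissue gives baseline status only. Section 2.1 lists potent Hedgehog inhibition among the findings that would support further study. At stake is how far the down-regulated proportion, and its association with PSA outcome, can be trusted as mechanistic evidence. The trial's efficacy decision is not at stake.

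**Working it through.** **1. The plan's own figures.** No sample size, power or precision is stated for GLI1, so there is no GLI1 figure to reproduce. The primary design in section 10.2 (22 then 40 patients, continue if more than 2 responses, reject at 8 or more) does reproduce by exact binomial calculation:
- P(X ≤ 2 | n = 22, p = 0.10) = 0.620, stated as 0.62.
- Power at 25% = 0.803, stated as 80%.
- Type I error at 10% = 0.0398, within the stated 0.05.

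None of these uses GLI1, so the point below leaves them unchanged.

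**2. Does the label reveal the visit?** The label carries date and protocol day. One biopsy precedes Day 1 and the other falls on day 28 ± 7, so the two cannot be confused. The laboratory stores what it receives until extraction, and the available text describes no recoding step.

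**3. How sensitive is the any-decrease rule?** Let the paired log change have symmetric (normal) noise and no drug effect, and let s be a systematic shift towards a decrease, in SDs of the paired change. The proportion called down-regulated is Φ(s). The values of s are assumptions, because the documents give no assay precision.

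| s | Φ(s) |
|---|---|
| 0 | 50% |
| 0.10 | 54% |
| 0.25 | 60% |
| 0.50 | 69% |

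Section 1.2.2.3 reports a decrease in 68% of men given 300 mg BID in the earlier trial. Since Φ⁻¹(0.68) = 0.47, a shift of about 0.47 SD with no effect would give the same figure. That is a yardstick for sensitivity and says nothing about what happened in that trial.

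**4. Separate runs.** Let w be the within-run SD of the paired difference and b the between-run SD, both in cycles and both assumed. Assaying the pair in different runs multiplies the variance by (w² + 2b²)/w²:
- w = 1.0, b = 0.2: (1.00 + 0.08)/1.00 = 1.08.
- w = 0.5, b = 0.5: (0.25 + 0.50)/0.25 = 3.0.

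Random run noise pulls a real effect towards 50%. A true within-run proportion of 68% would appear as Φ(0.468/√1.08) = Φ(0.450) = 67%, or Φ(0.468/√3.0) = Φ(0.270) = 61%. GAPDH normalisation may remove part of b. If baseline and week-4 samples fall systematically into different runs, the run difference is shared across men and acts like the shift in step 3.

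**5. Can pairs be held and run together?** The longest wait is 6 weeks before Day 1 (42 days) plus 28 + 7 = 35 days after it: 77 days, or 11 weeks. Appendix 3 gives stability of one year at -20°C, so this fits; the one-month limit at 4°C would not cover it. Enrolment is expected to last about 14 months (10.3), so one batch at the end would exceed one year at -20°C for the earliest samples. Several runs are therefore plausible, which makes a same-run rule for each pair useful.

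**The case against.** The strongest reply is that the documents nowhere say the assay staff are unmasked. Part of the skin shipping text in Appendix 3 is not in the public copy, and tubes could be recoded there or on accession. This stands: the label content is a fact, but knowledge of the visit at the time of assay is an inference.

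The contrast with other samples is also weaker than it looks. The UCSF log numbers are stated to be for confidentiality. The staining readers are blinded to outcome, and archived tissue has no visit to mask. Plasma for drug levels carries initials, day, time and protocol day as well (9.4), so the skin tubes follow an existing convention. A reader might infer that the plan breaks its own masking rule; it has no such rule for visit.

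A reader might also infer that initials and ID let the laboratory link tubes to PSA results. Johns Hopkins does enrol patients, but no text gives the laboratory PSA data, and study data are entered through secure accounts (section 12).

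Finally, the biopsy is optional (6.3.6), the endpoint is correlative, section 1.4 calls these findings exploratory, and qRT-PCR leaves less room for judgement than staining scores. All of that stands and limits the weight of the point. It does not answer why a label showing the visit should reach the assay laboratory when a coding mechanism already exists in the same appendix.

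**Conclusion.** The point holds as a cheap improvement. The labelling rule shows which biopsy is post-treatment, the available assay and analysis text states no recoding, masking of visit or same-run pairing, and the any-decrease rule has no margin to absorb a small shift.

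The documents do not support a claim that bias is present, or any particular size for it. The 54% to 69% range and the 1.08- to 3.0-fold variance ratios rest wholly on assumed shifts and SDs. The number of biopsy pairs is not given either. The primary endpoint, its sample size, power and decision rule are unaffected.

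Masking would not cure the rule itself: with symmetric noise and no effect, half of the men would still be counted as down-regulated.

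**What to change.** - **Appendix 3, section I:** label skin tubes only with a unique specimen log number assigned by the lead-centre coordinator, extending the mechanism in IV.A and stating that here it also serves to mask visit.
- **Key:** hold the list linking log number to patient, date, biopsy site and protocol day outside the assay laboratory. The Biomarkers Worksheet already records date and time; it should not travel with the tubes.
- **Section 9.2:** state that each man's two biopsies are extracted and run together, in coded order. The laboratory can be told which two log numbers form a pair without being told which came first.
- **Section 10.8.3:** state that visit is unmasked to derive fold change only after Ct values are final, so that reruns and exclusions are settled beforehand.

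The cost is log-number and key-holding work for at most 2 × 42 = 84 tubes if every man in the planned accrual of 42 consents, and storage of baseline samples for up to about 11 weeks, within the stated one-year stability at -20°C. No change to sample size, visits or the primary analysis is needed.
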